#### 4.4 END-OF-STUDY DEFINITION

A participant is considered to have completed the study if he or she has completed all baseline activities, watched the video through the VR headset during their teeth cleaning, complete the post-visit questionnaire, complete the 4-week text message program, complete the end-of-treatment questionnaire, and complete the two follow-up assessments (3-and 6 months after the end of treatment). The end of the study is defined as completion of the final assessment (6-months post end-of-treatment assessment) shown in the SoA, **Section 1.3**.

## 5 STUDY POPULATION

### 5.1 INCLUSION CRITERIA

To be eligible to participate in this study, human subjects must meet all of the following criteria, as applicable:

1. Provision of verbal consent to be screened (brief screening agreement).
2. Provision of verbal (or electronic) and dated informed consent to participate.
3. Patient of the Boston University, Henry M Goldman School of Dental Medicine, or the Tufts University, School of Dental Medicine with an upcoming dental hygiene appointment (dental prophylaxis or scaling and root planing) at the pre-doctoral, or the post-doctoral periodontal, patient treatment center for Boston University patients, or the comprehensive care clinics or the periodontal clinic for Tufts University patients, as indicated in EDR.
4. Male or female, 18 years of age or older.
5. Self-reported smoking 100 cigarettes or more in lifetime (not including e-cigarettes or vaping).
6. Self-reported smoking  $\geq 1$  cigarette in the preceding week (not including e-cigarettes or vaping).
7. Self-reported smoking cigarettes (not including e-cigarettes or vaping) 'some days', 'most days' or 'every day' in the preceding week.
8. Is able to understand written and spoken study materials.
9. Score of 'Never', 'Rarely' or 'Sometimes' on the validated single-item literacy screener ("How often do you need to have someone help you when you read instructions, pamphlets, or other written material from your doctor, dentist, or pharmacy?").
10. Self-reported visual capacity to watch a video as indicated by the score 'Some difficulty' or 'No difficulty' to: "How much difficulty do you have with your vision, even when wearing glasses?").
11. Self-reported ability to wear headphones that are inserted partially inside the ear.
12. Self-reported use of text messaging at least once in the preceding month.
13. Self-reported access to necessary resources for intervention: Cell phone capable of text messaging.
14. Live in Massachusetts.
15. Stated willingness to comply with text message program procedures (receive and respond to text messages for 4-weeks).

## 5.2 EXCLUSION CRITERIA

An individual who meets any of the following criteria will be excluded from participation in this study:

1. Participation in another treatment or intervention study for smoking cessation or research involving text messaging.
2. Current use of medications for smoking cessation or smoking reduction (nicotine replacement product, or non-nicotine medications) whether prescribed or not.
3. Failure to complete the pre-dental clinic appointment procedure before the start of the dental appointment (e.g., informed consent, opt-into the text message program and complete the baseline questionnaire).
4. Failure to show up to the scheduled dental appointment at the BU or TU clinic.
5. Previous participation in the UG3 Usability study or pre-award pilot study.

6. Inability to watch the video with the VR headset during the dental appointment.

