“Agile Health” (AH) is the company that will be programming and delivering our 4-week text message curriculum. Their database will contain the text messages including information on what text messages each participant has received, which texts participants have responded to, their actual responses, and feedback about individual messages. This database is HIPAA secure. Agile Health will not have access to the link between participant contact information and survey data. To ensure the highest level of data confidentiality, secure data transfer will occur through REDCap managed by the Boston University Biostatistics and Epidemiology Data Analytics Center (BEDAC) at the School of Public Health. Following a discussion with the BU director of health privacy and compliance, a BAA for this study is not required. Following a discussion with BUMC Information Security, study's co-investigator [name] is the appointed coordinator who will conduct quarterly access audits in consultation with Agile Health.

In order to verify that study participant have connected with the quitline, we need to share subject identifiers with National Jewish Health, which is the contracted vendor for the Massachusetts State quitline. The participants' information we share includes: 1) participant's name, 2) participant's telephone number, 3) participant's date of birth, and 4) participant's home address. We will also need to share the study enrollment date.

These identifiers constitute the minimum necessary data requested by National Jewish Health to enable them to verify in their database:

1. whether the participant made contact with the quitline; 2. whether the participant elected to start counseling; 3. the type of counseling the participant requested (e.g., phone, web or text message); 4. the number of counseling session the participant received; 5. whether the participant set a date to quit smoking; 6. whether the participant requested nicotine replacement products; and 7. whether nicotine replacement products were sent to the participant. Data sharing between the study team and National Jewish Health will only occur through a secure encrypted email system.

It is possible that some aspects of the assessments (e.g., answering questions about health habits and demographics) may be uncomfortable for some participants. However, participants will be informed that they may choose not to answer any questions that make them uncomfortable.

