## 4 STUDY DESIGN

### 4.1 OVERALL DESIGN

This study is a 2-arm, stage III randomized controlled efficacy trial. Three hundred seventy-six patients will be recruited at Boston University GSDM patient treatment center or TU comprehensive care (or Periodontal) clinic, and randomized to the Intervention group or the Control group. To account for participants who become ineligible post-informed consent (e.g., do not complete baseline activities, do not show up to dental visit) and thus are not randomized, we estimate that approximately 700 subjects will be enrolled. Our aim is to test whether the Intervention administered to dental patients during teeth cleaning increases contact with, and utilization of, EBTs. Smokers randomized to the Intervention group will receive: 1) the smoking cessation video intervention via VR headset during their teeth cleaning, 2) brochure about EBTs, and 3) 4-weeks of tailored, interactive, and automated text messages to motivate engagement with EBTs plus periodic text message reminders throughout the study. The Control group will watch a relaxation video through the VR headset during their teeth cleaning, receive a brochure about EBTs, and receive assessment-only text messages. We chose a 'relaxation video' because this topic is at least somewhat connected to the teeth cleaning experience (e.g., to ease dental anxiety and discomfort), rather than watching a video on general health and wellness, for example.

The Primary Objective is to test the efficacy of the Intervention vs. Controls in increasing contact with, and utilization of, EBTs over a 7-month period. Hypothesis 1.1 states: Participants randomized to the Intervention will be more likely to engage (make contact with) EBTs. Hypothesis 1.2 states: Participants randomized to the Intervention will have greater EBT utilization (e.g., more quitline counseling sessions, more days in the text message program).

The Secondary Objectives are: 1) To test the effect of the Intervention vs. Controls on quit attempts and on motivation to quit. Hypothesis 2 states: Participants in the Intervention will make more quit

Based on the NIH Behavioral and Social Intervention Clinical Trial Protocol Template v3.0 - 20180827

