### 6.3 MEASURES TO MINIMIZE BIAS: RANDOMIZATION AND BLINDING

We will conduct a stratified block randomization procedure with small, random size blocks. Participants will be randomized to one of two groups, Intervention or Control, after completing the baseline assessment, the in-clinic eligibility screener (to ensure that their smoking status has not changed since the screener), and receipt of brochure. Randomization will be stratified by motivation to quit (ready to quit smoking in 30 days vs. not ready to quit within 30 days). Only the PI, the project director, the statistician, and the clinic RAs (RAs who are setting up the video for each patient) will be unmasked to treatment condition. These RAs will not be involved in the collection of any outcome data. Because both the Intervention and Control groups will be watching a video, all dental providers will be able to be masked to participant's treatment condition. The RA who performs follow-ups and collection of saliva cotinine will be masked to treatment condition.

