- EBTs for smoking cessation will be operationalized as: 1) utilization of any EBT over the 7-month study period; 2) total number of EBTs utilization during the 7-month study period (ranging 0 to 4); 3) EBT utilization index score (UIS; obtained by first computing a proportion of utilization score for each of the EBTs for each participant, and then adding up the individual proportion scores; see section 9.4.1 for details); 4) combination of at least one form of non-pharmacologic EBT and at least one form of pharmacologic EBT over the 7-month study period.
- Quit smoking attempts (assessed at Time 4 – 6). The number of quitting smoking attempts participants have made, since last contact, that have lasted 24 hours or more and that were not due to hospitalization or illness.
- Motivation to quit smoking (assessed at Time 4 – 6). Participants' motivation to quit smoking within 30 days (yes vs no).
- Smoking abstinence (assessed at Time 4 – 6). Seven-day point-prevalence abstinence (7-day ppa) assessed by self-report of no smoking, not even a puff, in the past 7 days and salivary cotinine level < 15 ng/mL.
- Mediators of treatment effects (assessed at Time 2 – 6). Theoretically driven constructs hypothesized to mediate any observed intervention effect (EBT utilization, quit smoking attempts, motivation to quit, or smoking abstinence) include the social cognitive theory constructs of motivation, self-efficacy, and outcome expectancies.
- Moderators or treatment effects (assessed at baseline). Moderating factors include sex, race or ethnicity, perceived stress and readiness to quit smoking.

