#### 9.4.2 ANALYSIS OF THE PRIMARY ENDPOINT(S)

Aim 1 Hypothesis 1.1. Between group differences in any EBT utilization. The outcome is any EBT utilization over the 7-month study period, including use of the Quitline, clinic-based programs, NCI’s text message program, nicotine replacement therapy, other evidence-based medication (e.g., Bupropion, Varenicline). Quitline use will be based on objective usage data provided by National Jewish Health (the operator of the state's quitline contracted by the Massachusetts Tobacco Cessation and Prevention Program) (e.g., whether contact was made, number of counseling calls, whether patients set a quit date, whether nicotine replacement was requested and delivered to patients), and engagement with NCI’s text message program use (e.g., whether patients opted into the program, response rates, length of time in the program) will be obtained objectively from the program. Data on other EBT utilization (clinic-based counseling; receipt of smoking cessation meds outside of the quitline) will be based on self-report. This binary outcome will be analyzed through a logistic regression model, with the intervention effect described through an odds ratio and 95% confidence interval. We will control for age, gender, race/ethnicity, and variables identified through preliminary analyses as significantly differing between study groups.

Aim 1 Hypothesis 1.2. Dose of EBT utilization. The outcome is our UIS (described in 9.4.1) which summarizes participation in one or more EBTs (the quitline, nicotine replacement or other medications, the NCI SmokefreeTXT program, and clinic based programs). Multiple linear regression will be used to compare the Intervention vs. Control, controlling for age, gender, race/ethnicity, and variables identified through preliminary analyses as significantly differing between study groups. The intervention effect will be described through the slope, representing the difference in mean UIS for those in the Intervention vs. Control group.

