#### 9.4.3 ANALYSIS OF THE SECONDARY ENDPOINT(S)

Aim 1 Hypothesis 1.2. Dose of EBT utilization. As a secondary outcome, we will examine the total number of EBTs contacted over the 7-month study period (ranging from 0 to 4, for the quitline, any clinic-based program, NCI's text message program, and nicotine replacement or other medication). Participation in the Quitline or NCI's text message program will be based on usage data from the programs. Participation in clinic-based programs or use of smoking cessation medication outside of the quitline will be based on self-report. The number of EBTs utilized will be analyzed through Poisson regression for count data, with the intervention effect described through a rate ratio and 95% confidence interval describing the increased probability of engaging in an additional EBT for those in the Intervention vs. Control. We will control for age, gender, race/ethnicity, and variables identified through preliminary analyses as significantly differing between study groups.

Aim 1 Hypothesis 1.2. Dose of EBT utilization. As a secondary outcome, we will also create a binary indicator of use of a combination of counseling (including quitline, clinic-based programs, and the NCI's text message program) and medications over the 7-month study period. The Intervention will be compared to Control on this outcome through logistic regression, with the intervention effect summarized through an odds ratio and 95% confidence interval. We will control for age, gender, race/ethnicity, and variables identified through preliminary analyses as significantly differing between study groups.

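### Use of a quitline, SmokefreeTXT or clinic programme already under way at randomisation is not excluded, and the primary endpoint does not require a new start, so continued use can count as an event in either arm

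*Combined protocol and SAP*

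**What the plan says.** **Entry.** Section 5.2 excludes "Current use of medications for smoking cessation or smoking reduction (nicotine replacement product, or non-nicotine medications) whether prescribed or not". The nearest other criterion is "Participation in another treatment or intervention study for smoking cessation or research involving text messaging", which concerns research participation, not ordinary use of a service. Nothing else in 5.1 or 5.2 addresses EBT use at entry.

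**Endpoint.** Section 8.1 operationalises the first outcome as "utilization of any EBT over the 7-month study period", and 9.4.2 says "The outcome is any EBT utilization over the 7-month study period". Section 9.4.3 counts EBTs "ranging from 0 to 4, for the quitline, any clinic-based program", the NCI text programme, and medication. Sections 1.1 and 9.1 place the period after the dental appointment, which is when randomisation takes place (4.1).

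**Timing.** Screening takes place within about four weeks of the visit (8.1). Repeat screening is tied to appointments moved to 45 days after the screening form (5.4). On the day, participants complete "the in-clinic eligibility screener (to ensure that their smoking status has not changed since the screener"; 5.4 and 8.1 describe the same recheck, also in terms of smoking status.

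**Data on earlier use.** The baseline questionnaire covers past EBT utilization (1.3). The fixed covariates in 9.4.2 are age, gender and race/ethnicity; other variables enter only if they differ significantly between groups.

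**Vendor matching.** Of the quitline operator, 2.3.3 says "We will also need to share the study enrollment date". It mentions no randomisation date.

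**The concern.** The trial asks whether the Intervention drives smokers to make contact with treatment. A participant in mid-course with the quitline, SmokefreeTXT or a clinic on the visit day, who carries on afterwards, satisfies the binary endpoint as worded whichever video is shown. Such participants add events to both arms, pull the two proportions together on the odds scale and reduce power.

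The plan already screens out one kind of current user, those on medication, and leaves the other three. In the mediation analysis (9.4.9) it works from the first initiation of an EBT, so the order of events matters to its own reasoning. That idea does not reach the primary endpoint.

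A second, smaller gap concerns the date sent to the quitline operator. If it is the consent date, contacts made between consent and randomisation might come back in the match and be counted.

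**Working it through.** **1. Which current users can enter**

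| EBT type (9.4.3) | Current use excluded in 5.2? | Visit-day recheck described? |
|---|---|---|
| Quitline | No | No |
| Clinic-based programme | No | No |
| SmokefreeTXT | No | No |
| NRT or other medication | Yes | No |

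**2. Which of their use falls under the endpoint**

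- Use that ended before the appointment: outside the window (1.1, 9.1).
- Use under way at the appointment and continuing: inside the window, and no new-start rule removes it.
- A different EBT started after the appointment: an event on any reading.

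Only the second line is at issue.

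**3. What the enrollment date means**

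Section 4.1 says "we estimate that approximately 700 subjects will be enrolled", to allow for people who consent but are not randomised; there, enrolment comes before allocation. Section 5.5 also joins enrolment to consent. But the schedule in 1.3 puts consent in a column headed as before enrolment, and 5.4 and 8.1 call the screening stage pre-enrolment, which points to the clinic visit. The term is used both ways, and no section says how the vendor applies the date.

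**4. Reproducing the stated power**

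Inputs from 9.2: p_C = 0.227, p_I = 0.376, two-sided alpha 0.05, 455 × 0.8 = 364 evaluable, so n = 182 per arm.

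Power = Φ{[(p_I − p_C)√n − 1.96√(2p̄(1−p̄))] / √(p_C(1−p_C) + p_I(1−p_I))}, where p̄ is the mean of the two rates.

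With p̄ = 0.3015: (0.149 × 13.491 − 1.96 × 0.649) / 0.640 = 1.153, so power = 0.875. The plan states 0.87. The same method needs 296 in total for 0.80 power, against 300 stated. The odds ratio is 2.05. There is no arithmetic error in the plan.

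**5. Dilution**

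Let q be the share of each arm with ongoing use that continues (assumed; the documents give no value), and take the stated rates as new-start rates among the rest. If ongoing users count as events, the observed rate is q + (1 − q)p.

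| q (assumed) | Control | Intervention | Odds ratio | Power, n = 182 per arm |
|---|---|---|---|---|
| 0% | 22.7% | 37.6% | 2.05 | 0.875 |
| 2% | 24.2% | 38.9% | 1.99 | 0.853 |
| 5% | 26.6% | 40.7% | 1.90 | 0.818 |
| 10% | 30.4% | 43.8% | 1.78 | 0.756 |

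Power passes below 0.80 at q of about 6.5%.

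**6. Other readings of the stated rates**

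- Both 22.7% and 37.6% already include ongoing users: nothing is lost against the stated power.
- 22.7% includes them, but the odds ratio of 2.05 applies only to new starts: counting them gives power of 0.760 at q = 5% and 0.567 at 10%.

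Section 9.2 describes the rates as any EBT utilization and does not settle which reading applies.

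**7. What a new-start rule would do, on the reading in step 5**

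Suppose, at worst, that no ongoing user starts a further EBT, so all stay in the denominator as non-events. The rate is then (1 − q)p:

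- q = 5%: 21.6% v 35.7%, power 0.851 (0.818 when they count as events).
- q = 10%: 20.4% v 33.8%, power 0.823 (0.756 when they count as events).

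Leaving ongoing users out, with 182(1 − q) per arm, gives 0.858 and 0.839.

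**The case against.** Several points against the concern stand.

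- **The window.** A reader might infer that any treatment begun before randomisation counts. It does not: 1.1 and 9.1 confine the outcome to the period after the appointment. That continuing use counts is itself an inference from the literal wording; no section says so.
- **Medication.** A reader might infer that current medication use is permitted. It is an exclusion, and 7.2 allows discontinuation when an exclusion is newly developed or newly recognised. The items on the in-clinic screener are not reproduced, and 5.4 gives its purpose as confirming that participants remain eligible. The gap is only that no medication recheck is described. The quitline also supplies NRT (2.2), so some of its current users would be excluded on that ground.
- **Bias.** A chance imbalance in ongoing users might be read as a route to a false effect. Under 1:1 randomisation it is ordinary sampling error, already covered by alpha.
- **Vendor date.** The text does not show that contacts before allocation will be returned, only that the term is ambiguous.
- **Inducement.** Ongoing users can still respond. They can add an EBT or persist longer, and Hypothesis 1.2 concerns more sessions and more days. A rule that struck continued use out of the utilization index score (UIS) would discard an effect the trial sets out to test.
- **Size.** Prevalence is unknown, and power stays above 0.80 up to about 6.5% on the main reading.

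These points narrow the concern but do not supply the missing rule. The window bounds when use occurs, not when it began. Baseline past-use data are collected, but no stated rule applies them to the endpoint, and adjustment depends on a significant imbalance.

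**Conclusion.** The concern holds as a gap in the endpoint definition. Current use of three of the four EBT types is not excluded, no recheck beyond smoking status is described for the visit day, and nothing separates continued use from a new start. The consequence to expect is a smaller odds ratio and less power.

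The size cannot be fixed from the documents. For an assumed 2% to 10% of ongoing users in each arm, with the stated rates taken as new-start rates, the odds ratio falls to between 1.99 and 1.78 and power to between 0.85 and 0.76. The loss against the stated power is nil if both rates already include these users, and larger if only the control rate does. The vendor-date point is a possibility to close off, not an established error.

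**What to change.** In 8.1, 9.4.2 and the SAP, which 9.4.1 says is still to be completed before unblinding:

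1. For the binary endpoint and the EBT count, count only an EBT started after the randomisation date and time. Continuing one already in use does not count; starting a different one does.
2. Give the quitline operator the randomisation date, and count quitline and SmokefreeTXT contacts only from that date.
3. For the UIS, count only sessions, days and medication use after randomisation. Keep continued use in the score, and adjust for baseline EBT use.
4. Identify ongoing users from the baseline past-utilization answers and vendor dates. For participants not yet randomised, add one item on current use of all four EBT types to the in-clinic screener. Run a sensitivity analysis excluding ongoing users.

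**Cost.** Endpoint wording, a different date in the vendor file and one eCRF item. Event rates may be slightly lower. Ongoing self-reported use will be identified imperfectly among those already randomised, because a question on past use may not isolate current use. The screener item has limited reach: this version is dated September 2024 and the study ends on 31 July 2025 (1.1), so a full seven-month follow-up requires randomisation by about the end of December 2024. The endpoint rule and the vendor date matter more.
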